10.8.2. Local and Systemic Reactions

Local and systemic reactions are collected by the investigator pre and post vaccination on Day 0. In addition, local and systemic reactions are captured in the participant diary card on Days 1, 2 and 3. The worst incidence of each local and systemic reaction post vaccination for each participant will be summarised.

The size of swelling (induration) and redness (erythema) is measured in mm. The largest injection site swelling post vaccination and the largest area of redness post vaccination will be summarised.

Pain and warmth at the site are collected on a five-point scale including, none (grade 0), no interference with daily activities (grade 1), some interference with daily activities (grade 2), significant interference preventing daily activities (grade 3), and ER visit or hospitalisation visit (grade 4). The worst degree of pain and separately worst degree of warmth post vaccination will be summarised.

The severity of redness and swelling will be derived for each participant as:

- <2.5cm – Grade 0,
- 2.5 to 5cm – Grade 1,
- 5.1 to 10cm – Grade 2,

- >10cm – Grade 3.

The number and percentage of participants with each degree of worst pain, worst warmth, worst redness and worst swelling will be summarised; the denominator will be the number of participants in the safety analysis set.

Systemic reactions include muscle ache (myalgia), fatigue, headache, nausea, feverishness, chills, joint ache (arthralgia) and malaise. Each of these items are collected on a five-point scale including, none (grade 0), no interference with daily activities (grade 1), some interference with daily activities (grade 2), significant interference preventing daily activities (grade 3), and ER visit or hospitalisation visit (grade 4). The worst reaction will be summarised for each systemic reaction as the number and percent of participants, the denominator will be the number of participants in the analysis set.

The temperature will be graded as:

- <38.0 – Grade 0,
- 38.0 to 38.4 – Grade 1,
- 38.5 to 38.9 – Grade 2
- 39.0 to 40.0 – Grade 3
- >40.0 – Grade 4

Worst temperature will then be summarised, along with the worst temperature severity. Only the temperature recorded as part of the local and systemic reactions (i.e. on the corresponding CRF page or subject diary) will be summarised in this table.

Additionally, a table will summarise the number of participants who experienced any of the symptoms.

Missing data will not be imputed and diary card data will be summarised as collected.

All Diary Card and Investigator reported local and systemic reactions will be listed.

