6.2 Treatment Day Assessments (Day 0)

The following will be performed pre-vaccination:

- Re-check of eligibility criteria
- A urine pregnancy test will be performed
- Blood samples will be taken for haematology (including PT/INR and aPTT), biochemistry and LFTs

- A full physical examination will be performed
- Vital signs (pulse rate, blood pressure and temperature) will be measured
- A baseline assessment of local and systemic reactogenicity will be performed
- Blood samples will be taken for immunogenicity assessments (including neutralising antibodies for cohorts 5 and 6 only)

Participants will then receive study vaccine by intramuscular injection according to [Table 1](#). All participants will be assessed for at least 30 minutes in the clinic after receiving the vaccine injection in case of immediate adverse events. The first participant in each cohort will be observed for 1 hour.

The following will be performed post-vaccination:

- The vaccination site will be covered with a sterile dressing during the observation period; it will then be removed and disposed of as GMO waste
- Vital signs (pulse rate, blood pressure and temperature) will be measured at the end of the observation period
- Local and systemic reactogenicity will be assessed at the end of the observation period
- On Day 0, an eDiary, tape measure and thermometer will be provided to perform self-assessment of local and systemic reactogenicity for 3 days after the vaccination. On Day 0 participants will be reminded to do the following daily for the next 3 days:
 - Take and record their temperature
 - Measure and record the size of vaccination site redness
 - Assess the other solicited adverse events listed in the eDiary

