Every effort should be made by the Investigator to determine the existence of any pre-existing conditions (e.g. headache in adults or rashes in infants on study Day 0 with onset prior to study vaccination) that must be taken into consideration when assessing causal relationship of an adverse event. Pre-existing conditions should be recorded in the eCRF as baseline history and substantiated by appropriate source documentation. Intermittent conditions such as headaches in adults or irritability in infants may not be present on study Day 0 but may represent an adverse event if the intensity or duration of the event is worse than usual following study vaccine.

8.2.3.3 *Action Taken with Study Vaccine*

The action taken with the study vaccine will be recorded as None, as only one dose is given.

8.2.3.4 *Assessment of Outcome*

The outcome of the adverse event will be assessed as:

- Recovered/resolved
- Recovered/resolved with sequelae
- Not recovered/resolved
- Unknown
- Fatal

8.2.4 *Reporting Requirements and Procedures for Serious Adverse Events*

All SAEs are reported to the Sponsor for the entire study period. Suspected, unexpected, serious adverse reactions are reported even after the study is over, if the Sponsor, local Medical Monitor or Principal Investigator becomes aware of them. The study centre will be provided with specific reporting procedures including the SAE paper form and any supplemental reporting forms to be used. SAEs will be reported on the SAE paper form and the adverse event eCRF using a recognised medical term or diagnosis that accurately reflects the event.

SAEs will be assessed for severity, causal relationship to the study vaccine or alternative aetiology by the Sponsor and Investigator. The onset and resolution dates of the event and medical care taken in response to the event will be documented. If the event has not resolved by the end of the study is enrolled into, it will be documented as "ongoing" on the eCRF, however, follow-up of the SAE must continue until resolved or the condition has stabilised. Information recorded on the eCRF must be substantiated in the source documents.

The SAE form for that event must be completed by the Investigator, within 24 hours of the study centre becoming aware of the event. The SAE form should be completed with all information known at the time and scanned and emailed to the local Medical Monitor and to [REDACTED]

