10. PLANNED STATISTICAL METHODS

10.1. Statistical Considerations

10.1.1. General definitions

Definition of baseline

Baseline is defined as the last non-missing value for a participant, for the particular parameter, that is prior to the administration of study vaccine.

Study completion definition

A participant completes the study by engaging in study activities up to and including the End of Study Visit at Day 168 (+/- 7 days), for cohorts 1 to 4, and Day 84 (+/- 7 days) for cohorts 5 and 6.

Treatment Group

There are six treatment groups in this study; the Healthy Participants and CHB participants are split into high and low doses of vaccination. Healthy participants in the high dose group are further split into those with no previous exposure to ChAdOx1 vectored vaccines, those with recent previous exposure to Covid-19 ChAdOx1 vectored vaccine (cohort 5) and those with previous exposure to Covid-19 mRNA based vaccines (cohort 6).

Results below limit of detection and quantification

Immunogenicity results that are below the limit of quantification or detection (i.e. reported as <X or BLQ) will be replaced by 0 for any summaries but will be listed as reported.

Geometric Mean and Standard Deviation

The geometric mean (GM) and geometric standard deviation (GSD) are obtained by calculating the mean and SD of the log-transformed data and back-transforming these. If there are any zero values in the data a small number should be added to all values before log-transformation and then subtracted from the resulting GM. This small number will be 1 unless stated otherwise.

GM = antilog (mean (log(value + S))) – S, where S is a small number, relative to the non-zero results.

GSD = antilog(standard deviation(log(value + S)))

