10.8.4. Vital Signs

Vital signs parameters (temperature (C), pulse rate (bpm), systolic blood pressure (mmHg) and diastolic blood pressure (mmHg)) will be listed.

Toxicity grades will be calculated for relevant vital sign parameters, as per Appendix 1 of the study protocol (Section **Error! Reference source not found.**). Shift tables will be presented showing changes in each toxicity grade from the baseline grade to the maximum post-baseline grade for each treatment group.

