Feverishness	n (%)	xx (xx, x)	xx (xx, x)	xx (xx, x)	xx (xx, x)	xx (xx, x)	xx (xx, x)	xx (xx, x)
Chills	n (%)	xx (xx, x)	xx (xx, x)	xx (xx, x)	xx (xx, x)	xx (xx, x)	xx (xx, x)	xx (xx, x)
Joint Ache	n (%)	xx (xx, x)	xx (xx, x)	xx (xx, x)	xx (xx, x)	xx (xx, x)	xx (xx, x)	xx (xx, x)
Malaise	n (%)	xx (xx, x)	xx (xx, x)	xx (xx, x)	xx (xx, x)	xx (xx, x)	xx (xx, x)	xx (xx, x)

The distinct number of participants who experienced reactions of Grade 1 or higher between Day 0 and Day 3 is presented. The reactions on Day 0 are recorded by the investigator, whereas the reactions on Day 1 – Day 3 are recorded by the participant in a diary card. Percentages are based on the number of non-missing observations. All COVID-19 vaccinated participants were given the high dose of ChAdOx1-HBV vaccine.

Table 14.3.4
Shift Summary of Haematology Results by Maximum Toxicity Grade
Safety Analysis Set

Lab Parameter	Baseline Grade [n (%)]	Maximum Post-baseline Grade				Total	Missing
		Grade 0	Grade 1	Grade 2	Grade 3		
Lab Parameter 1							
Grade 0	xx (xx.x)	xx (xx.x)	xx (xx.x)	xx (xx.x)	xx (xx.x)	xx (xx.x)	xx
Grade 1	xx (xx.x)	xx (xx.x)	xx (xx.x)	xx (xx.x)	xx (xx.x)	xx (xx.x)	xx
Grade 2	xx (xx.x)	xx (xx.x)	xx (xx.x)	xx (xx.x)	xx (xx.x)	xx (xx.x)	xx
Grade 3	xx (xx.x)	xx (xx.x)	xx (xx.x)	xx (xx.x)	xx (xx.x)	xx (xx.x)	xx
Grade 4	xx (xx.x)	xx (xx.x)	xx (xx.x)	xx (xx.x)	xx (xx.x)	xx (xx.x)	xx
Total	xx (xx.x)	xx (xx.x)	xx (xx.x)	xx (xx.x)	xx (xx.x)	xx (xx.x)	xx
Missing	xx	xx	xx	xx	xx	xx	xx
Lab Parameter 2							
Grade 0	xx (xx.x)	xx (xx.x)	xx (xx.x)	xx (xx.x)	xx (xx.x)	xx (xx.x)	xx
Grade 1	xx (xx.x)	xx (xx.x)	xx (xx.x)	xx (xx.x)	xx (xx.x)	xx (xx.x)	xx
Grade 2	xx (xx.x)	xx (xx.x)	xx (xx.x)	xx (xx.x)	xx (xx.x)	xx (xx.x)	xx
Grade 3	xx (xx.x)	xx (xx.x)	xx (xx.x)	xx (xx.x)	xx (xx.x)	xx (xx.x)	xx
Grade 4	xx (xx.x)	xx (xx.x)	xx (xx.x)	xx (xx.x)	xx (xx.x)	xx (xx.x)	xx
Total	xx (xx.x)	xx (xx.x)	xx (xx.x)	xx (xx.x)	xx (xx.x)	xx (xx.x)	xx
Missing	xx	xx	xx	xx	xx	xx	xx
...							

Note: Total is the number of subjects with at least 1 post-baseline result, and percentages are based on the row total.
Note: Baseline is defined as the nearest assessment completed prior to vaccination.

Programming note(s):

(1) The table will have separate pages for each cohort, i.e. Healthy Participants high dose, CHB Participants low dose, CHB Participants high dose, Healthy Participants low dose, Healthy Participants - Covid-19 Vaccinated: mRNA.

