				Nausea	ddmmyy	xx.x	yes/no	xx.x	xx.x	yes/no	xx.x	xx.x	xx.x	xx.x
				Feverishness	ddmmyy	xx.x	yes/no	xx.x	xx.x	yes/no	xx.x	xx.x	xx.x	xx.x
				Chills	ddmmyy	xx.x	yes/no	xx.x	xx.x	yes/no	xx.x	xx.x	xx.x	xx.x
				Joint ache	ddmmyy	xx.x	yes/no	xx.x	xx.x	yes/no	xx.x	xx.x	xx.x	xx.x
				Generally feeling unwell	ddmmyy	xx.x	yes/no	xx.x	xx.x	yes/no	xx.x	xx.x	xx.x	xx.x
				Medication Taken	ddmmyy	xx.x	yes/no	xx.x	xx.x	yes/no	xx.x	xx.x	xx.x	xx.x
				Visit to A&E	ddmmyy	xx.x	yes/no	xx.x	xx.x	yes/no	xx.x	xx.x	xx.x	xx.x

* = indicates worst post-baseline incidence/highest value
All local and systemic reactions recorded on Day 0 (pre and post) are as recorded by the investigator. The reactions recorded Day 1 to day 3 are recorded by the participant in a diary card.

Severity: 0 = None, 1 = No interference with daily activities, 2 = Some interference with daily activities, 3 = Significant interference with daily activities, 4 = ER visit or hospitalization.
Medication Taken and Visit to A&E are yes if these were recorded as such for any symptom at the specific timepoint.

Programming note: place a "*" against the worst post-baseline incidence/highest value for each reaction for each participant, in the event of a tie the first one should be flagged. If all 0 then none should be flagged
Programming note: The numeric grade should be displayed in the listing

Listing 16.2.6.1.2
Diary Card: Medications Taken

Cohort	Participant	Study Day	Date/time	Symptom(s)	Medication Taken	Medication Name	Dose taken (units)	Number of times taken	Additional symptoms this medication refers to
xxxxxx	xxxxxx	0/1/2/3	ddmmmyyy hh:mm	xxxxxx	xxxxxx	xxxxxx	xxxx	xx	xxxxx

Programming Note: Only display details for the days on which medication was taken. If no medication taken throughout then this listing will be empty
Programming Note: Symptoms should list all of the symptoms that this medication was listed against on the specific day it was taken.

Listing 16.2.6.2
HBV Disease Markers

Cohort	Participant	Visit	Date/time	Parameter	Result	Comments
xxxxxx	xxxxxx	Day x	ddmmyyy / hh:mm	HBV DNA HBV pRNA Hepatitis B surface Antibody Hepatitis B surface Antigen Hepatitis B core Antibody Hepatitis B core Antigen Hepatitis B e Antibody Hepatitis B e Antigen		

Multi-parameter index
HBeAg loss
HBsAg Loss
HbeAg and HBsAg seroconversion

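### The systemic and any-reaction tables ignore the pre-dose grade taken on Day 0, so an unchanged pre-existing Grade 1-2 symptom is tabulated as a reaction

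*SAP*

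**What the plan says.** Protocol 6.2 lists among the Day 0 procedures before vaccination: "A baseline assessment of local and systemic reactogenicity will be performed". SAP 10.8.2 agrees: "Local and systemic reactions are collected by the investigator pre and post vaccination on Day 0". Days 1 to 3 come from the participant's diary. For the summary the SAP then says: "The worst incidence of each local and systemic reaction post vaccination for each participant will be summarised".

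The table shells follow that rule. Table 14.3.3.2 shows the worst grade of each systemic symptom. The footnote to Table 14.3.3.3 reads: "The distinct number of participants who experienced reactions of Grade 1 or higher between Day 0 and Day 3 is presented". Neither shell has a pre-dose row or column, a shift from pre-dose, or a condition that the symptom be new or worse. Pre-dose grades are shown only in Listing 16.2.6.1.1, whose footnote says: "All local and systemic reactions recorded on Day 0 (pre and post) are as recorded by the investigator".

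Other safety data are handled differently. SAP 10.1.1 gives a general definition: "Baseline is defined as the last non-missing value for a participant, for the particular parameter, that is prior to the administration of study vaccine". SAP 10.8.4 applies it to vital signs, and 10.8.3 does the same for laboratory values: "Shift tables will be presented showing changes in each toxicity grade from the baseline grade to the maximum post-baseline grade for each treatment group".

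**The concern.** Headache, fatigue, myalgia and malaise are common complaints with many causes besides a vaccine. A placebo or unvaccinated group would normally show how much of the observed rate is background. This trial has none, so each participant's own pre-dose grade is the only untreated reference inside the study. It is collected for every solicited symptom and then left out of the tables.

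Protocol 3.3 explains that solicited symptoms are gathered to see whether they are more frequent or more severe than earlier experience with similar vectors would suggest. A rate that includes symptoms already present before the injection serves that purpose less well. In groups of 5 and 6, a single participant changes the percentage visibly.

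**Working it through.** The plan states no figure to reproduce. The check is a reading of the counting rule, followed by simple arithmetic on its weight.

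**1. Follow one participant through the outputs.** Suppose, for illustration, a Grade 1 headache before dosing, Grade 1 again after dosing on Day 0 and on Day 1, and none on Days 2 and 3.

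| Output | Result |
|---|---|
| Table 14.3.3.2 | Headache, worst grade 1 |
| Table 14.3.3.3 | Counted under headache, any systemic reaction and any reaction |
| Listing 16.2.6.1.1 | 1, 1, 1, 0, 0; the first worst post-baseline value is flagged, with no comparison to pre-dose |
| Shift method of SAP 10.8.3 and 10.8.4, if it were applied | Grade 1 to Grade 1, no change |

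The adverse event rules also differ. Under SAP 10.8.1, an adverse event with onset before the vaccination date is classed as pre-treatment and is not treatment-emergent.

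**2. Can this happen under the protocol?** Yes. Protocol 4.3.1.1 defers vaccination for moderate or severe acute illness but allows it with minor illness. Low-grade systemic symptoms on Day 0 are therefore foreseeable.

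**3. Is there another background reference?** No. Table 1 in both documents gives ChAdOx1-HBV to every cohort, and the design is open-label and non-randomised.

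**4. Weight of one case.** With all members of a group contributing data, one unchanged carry-over adds 100/n percentage points to that symptom's row:

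| Group | n | 100/n |
|---|---|---|
| Cohorts 1 and 2 | 5 | 20.0 |
| Cohorts 3 and 4 | 6 | 16.7 |
| Cohorts 5 and 6 | 15 | 6.7 |
| Total | 52 | 1.9 |

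In the any-systemic and any-reaction rows, the same participant adds a spurious count only if no other qualifying reaction is new or worse.

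**5. Which outputs are exposed?**
- *Grade 3 or higher reactions* (a primary endpoint component). For carry-over, the symptom would have to prevent daily activities before dosing, which is hard to square with the deferral rule in Protocol 4.3.1.1.
- *Table 14.3.3.1.* Pain, warmth, redness or swelling at an injection site is improbable before the injection.
- *Tables 14.3.3.2 and 14.3.3.3.* The Grade 1-2 systemic rows and the rows built on them are where the effect falls.

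**The case against.** The strongest reply is that counting every post-dose symptom errs toward over-reporting, which is a defensible choice in a first-in-human safety study. The pre-dose grades are not lost: Listing 16.2.6.1.1 sets them beside the later grades, and with 52 participants each case can be checked. A new-or-worse rule used alone could also hide a reaction that merely prolongs an existing symptom. All of this stands. It is why the planned count should stay, but it is no reason to leave the comparison out of the tables.

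Five stronger readings are tempting, and the documents do not support them.

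- *That the primary Grade 3 or higher count is inflated.* Protocol 4.3.1.1 makes a pre-dose symptom of that grade unlikely.
- *That the SAP breaks a protocol rule that a pre-existing symptom counts only if it worsens.* Protocol 8.2.3.2 does say that a condition "may represent an adverse event if the intensity or duration of the event is worse than usual following study vaccine". That sentence concerns intermittent conditions that may be absent on Day 0, and it names duration as well as intensity. For symptoms present on Day 0, the section asks the investigator to weigh them when judging causality. It sets no counting rule for tables.
- *That the pre-dose record itself enters the count.* The footnotes mention Day 0 to Day 3 without saying after vaccination, but the text of SAP 10.8.2 does say so. This is a wording gap.
- *That some 3 to 10 participants are falsely counted as reactors.* That range comes from assuming that 5% to 20% carry a symptom over (52 × 0.05 = 2.6; 52 × 0.20 = 10.4). Neither rate is in the documents. Even on that assumption it is an upper bound, because someone with any other new symptom is a true reactor.
- *That dose or CHB-versus-healthy contrasts are distorted in a known direction.* Nothing in the documents shows that background symptoms differ between groups, and no formal comparison is planned.

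**Conclusion.** The point holds for Grade 1-2 systemic symptoms in Tables 14.3.3.2 and 14.3.3.3. An unchanged pre-existing symptom is tabulated as a reaction, although the grade needed to recognise it is already collected and the SAP already uses baseline grades for laboratory and vital-sign data. SAP section 11 gives no reason for the difference.

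Each case is worth 20.0 percentage points in a symptom row for a group of 5 and 16.7 for a group of 6, assuming complete data in the group. The number of cases cannot be estimated from the documents. The conclusion does not depend on that number, because it rests on the counting rule, the allowance for minor illness and the absence of an unvaccinated arm. This is an inexpensive improvement to the descriptive tables and does not challenge the primary safety conclusion.

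**What to change.** - **SAP 10.8.2:** keep the worst post-vaccination count as planned. Add that the pre-dose grade of each systemic symptom will be shown, together with a second count limited to symptoms that are new or higher in grade than pre-dose.
- **Tables 14.3.3.2 and 14.3.3.3:** add the pre-dose grade, or a shift from pre-dose to worst post-dose grade in the style of Tables 14.3.4 to 14.3.6. Place the new-or-worse line beneath the existing one.
- **Footnotes of Tables 14.3.3.1 to 14.3.3.3:** insert the words post vaccination, so that they match SAP 10.8.2.

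The cost is SAP wording and a little more programming; the data are already collected. The drawback is that the second line misses a reaction that only prolongs a symptom at the same grade. Such a case remains in the first line, so no safety information is removed.

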7.2.2.1 *Exploratory Analysis in Blood Samples*

HBV-specific CD4+ and T cell subsets within PBMC will be further defined by phenotypic markers of activation, differentiation and memory. Peripheral blood mononuclear cells will also be used in IFN- γ ELISpot assays to determine the breadth of HBV-specific T cell responses (defined by number of peptide pools or individual peptides recognised). These data may be used to build immunologic models of the immune system.

Blood samples will be used for extraction of RNA and subsequent unbiased analysis of innate immune responses before and after vaccination by RNA sequencing.

Serum blood samples will be used for analysis of pgRNA and HBcAg.

7.2.2.2 *Exploratory Analysis in Liver Fine Needle Aspirates*

Liver fine needle aspirate assays will be used to quantify and characterise intrahepatic immune and parenchymal cells and/or HBV DNA and RNA transcripts. The local immune landscape at Day 84 will be compared with baseline. Additional exploratory assessments may be performed. This is an optional procedure for CHB participants only. The Principal Investigator will provide a separate consent for this procedure which will explain the procedure in full and all associated risks.

7.3 **Safety Assessments**

7.3.1 *Adverse Events*

Recording and reporting of adverse events is described in detail in [Section 8.2](#).

7.3.1.1 *Solicited Adverse Events*

Solicited adverse events are events the participant is specifically asked about. These adverse events are commonly observed soon after receipt of vaccines and relate to local and systemic signs and symptoms. Solicited adverse events will be collected for 3 days post-vaccination¹. These will be recorded daily in the eDiary for all participants.

For this study, solicited adverse events to be collected include:

- Vaccination site reactions: pain, induration, warmth, erythema (redness)
- Systemic adverse events: feverishness, chills, myalgia, fatigue, headache, nausea, arthralgia, malaise

Participants will be asked to record the presence of these symptoms and grade the severity as described in [Section 8.2.3.1](#). Oral temperature will be measured using the thermometer provided and the diameter of induration will be measured with the tape measure provided.

7.3.1.2 *Unsolicited Adverse Events*

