The reporting period for all adverse events begins on the date the informed consent is signed. Solicited adverse events are recorded in the eDiary up to 3 days post-vaccination. All other events are recorded in the eCRF up until Day 28. All SAEs and or Adverse events of special interest are recorded until at least 168 days after the last study vaccination dose and for all serious or study vaccine-related adverse events until these are resolved or until participant contact discontinues.

Adverse event information will be collected at study visits and participant will be instructed to call study team members to report any abnormalities during the intervals between study visits and to come to the study centre if medical evaluation is needed and the urgency of the situation permits.

8.2.3 *Recording and Assessment of Adverse Events by the Investigator*

Solicited adverse events are recorded in the eDiary up to 3 days post-vaccination. All other adverse events are recorded in the eCRF up to until Day 28. All adverse events, both those observed by study team members and those spontaneously reported by the participant, will be recorded in the eCRF. Solicited adverse events will be reported using pre-defined terms. Unsolicited adverse events will be reported using a recognised medical term or diagnosis that accurately reflects the event.

Adverse events will be assessed by the Investigator, or a medically qualified study team member, for severity, relationship to study vaccine, action taken, outcome and whether the event meets criteria as an SAE according to the following guidelines:

8.2.3.1 *Assessment of Severity*

The severity of adverse events will be graded according to the toxicity table in [Appendix 1](#). The scale shown in [Table 3](#) will be used to assess severity of adverse events not listed in [Appendix 1](#).

Table 3 Severity Grading of Adverse Events not listed in the Toxicity Table for Clinical and Laboratory Abnormalities

Grade	Severity	
1	Mild	Asymptomatic or mild symptoms; clinical or diagnostic observations only; or intervention not indicated; no disruption of normal daily activity.
2	Moderate	Minimal, local, or non-invasive intervention indicated; discomfort sufficient to reduce or affect daily activity.
3	Severe	Severe or medically significant, but not immediately life-threatening; hospitalisation or prolongation of hospitalisation indicated; inability to work or perform normal daily activity.

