Tenderness	Mild discomfort to touch	Discomfort with movement	Significant discomfort at rest	ER visit or hospitalization
Erythema/Redness *	2.5 – 5 cm	5.1 – 10 cm	> 10 cm	Necrosis or exfoliative dermatitis
Induration/Swelling **	2.5 – 5 cm and does not interfere with activity	5.1 – 10 cm or interferes with activity	> 10 cm or prevents daily activity	Necrosis

* In addition to grading the measured local reaction at the greatest single diameter, the measurement should be recorded as a continuous variable.

** Induration/Swelling should be evaluated and graded using the functional scale as well as the actual measurement.

Contains Nonbinding Recommendations

Vital Signs *	Mild (Grade 1)	Moderate(Grade 2)	Severe (Grade 3)	Potentially Life Threatening (Grade 4)
Febrile (°C) **	38.0 – 38.4	38.5 – 38.9	39.0 – 40	> 40
	100.4 – 101.1	101.2 – 102.0	102.1 – 104	> 104
Tachycardia - beats per minute	101 – 115	116 – 130	> 130	ER visit or hospitalization for arrhythmia
Bradycardia - beats per minute***	50 – 54	45 – 49	< 45	ER visit or hospitalization for arrhythmia
Hypertension (systolic) - mm Hg	141 – 150	151 – 155	> 155	ER visit or hospitalization for malignant hypertension
Hypertension (diastolic) - mm Hg	91 – 95	96 – 100	> 100	ER visit or hospitalization for malignant hypertension
Hypotension (systolic) - mm Hg	85 – 89	80 – 84	< 80	ER visit or hospitalization for hypotensive shock
Respiratory Rate - breaths per minute	17 – 20	21 – 25	> 25	Intubation

* Subject should be at rest for all vital sign measurements.

** Oral temperature, no recent hot or cold beverages or smoking.

*** When resting heart rate is between 60 – 100 beats per minute. Use clinical judgement when characterizing bradycardia among some healthy subject populations, for example, conditioned athletes.

Systemic (General)	Mild (Grade 1)	Moderate(Grade 2)	Severe (Grade 3)	Potentially Life Threatening (Grade 4)
Nausea/vomiting	No interference with activity or 1 – 2 episodes/24 hours	Some interference with activity or > 2 episodes/24 hours	Prevents daily activity, requires outpatient IV hydration	ER visit or hospitalization for hypotensive shock
Diarrhea	2 – 3 loose stools or < 400 gms/24 hours	4 – 5 stools or 400 – 800 gms/24 hours	6 or more watery stools or > 800gms/24 hours or requires outpatient IV hydration	ER visit or hospitalization

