7. STUDY ENDPOINTS

7.1. Primary Safety Endpoint(s)

Incidence of safety and reactogenicity events:

- Adverse events and/or adverse events leading to study discontinuation
- Serious adverse events
- Grade ≥ 3 local and systemic reactions

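### The SAP grades injection-site swelling by diameter alone, while the protocol's scale grades it by size or function, so the swelling row can understate Grade 3

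*SAP*

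**What the plan says.** The primary safety endpoint includes "Grade ≥ 3 local and systemic reactions" (SAP 7.1).

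Protocol 8.2.3.1 sets the scale: "The severity of adverse events will be graded according to the toxicity table in" Appendix 1. Protocol 7.3.1.1 extends it to solicited reactions, which include induration: "Participants will be asked to record the presence of these symptoms and grade the severity as described in" Section 8.2.3.1.

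For induration/swelling, Appendix 1 uses size or function. Grade 2 is "5.1 – 10 cm or interferes with activity" and Grade 3 is "> 10 cm or prevents daily activity". Grade 4 is necrosis. A footnote adds: "Induration/Swelling should be evaluated and graded using the functional scale as well as the actual measurement". Erythema is graded by size alone up to Grade 3, and its Grade 4 is necrosis or exfoliative dermatitis.

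SAP 10.8.2 has one rule for both signs: "The severity of redness and swelling will be derived for each participant as" four diameter bands, for example "5.1 to 10cm – Grade 2", ending with Grade 3 above 10 cm. It has no functional criterion and no Grade 4. The five-point functional scale is kept for pain, warmth and the systemic symptoms.

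The Table 14.3.3.1 shell nevertheless has Grade 4 rows for swelling and redness. Its only severity key is functional, running from no interference with activities to an emergency visit or hospitalisation. Listing 16.2.6.1.1 shows only presence and size for swelling. SAP Section 11 lists two changes from the protocol, and this is not one of them.

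**The concern.** The SAP applies a narrower rule than the scale the protocol adopts, to a component of a primary endpoint, without saying so. Because the omitted criterion can only raise a grade, any discrepancy runs one way, towards milder reactions.

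The output would also mislead by its labelling. A reader of Table 14.3.3.1 would take a swelling Grade 2 to mean some interference with activities, as the key says, when it was assigned from a diameter.

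The swelling row matters because the table list in SAP 13.2 has no participant-level count of Grade 3 or higher reactions, and Table 14.3.3.3 counts Grade 1 or higher. Grade 3 reactions will be read item by item from Tables 14.3.3.1 and 14.3.3.2.

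**Working it through.** The plan states no figure to reproduce. The check sets the two rules side by side and then asks what one reclassified participant does to a rate.

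**Rules.** Inputs are the Appendix 1 induration/swelling row and the SAP 10.8.2 bands.

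- Protocol grade (Grades 0 to 3) = the worse of the size grade and the functional grade.
- SAP grade = the size grade.

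The worse of two grades is never below either one, so the SAP grade is never above the protocol grade.

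| Diameter | SAP grade | Protocol grade, interferes with activity | Protocol grade, prevents daily activity |
|---|---|---|---|
| under 2.5 cm | 0 | 2 | 3 |
| 2.5 to 5 cm | 1 | 2 | 3 |
| 5.1 to 10 cm | 2 | 2 | 3 |
| over 10 cm | 3 | 3 | 3 |

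The Grade 3 discrepancy therefore covers every swelling of 10 cm or less that prevents daily activity. A swelling under 2.5 cm that affects activity also disappears from the swelling row of Table 14.3.3.3, because the SAP grades it 0.

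**Redness.** The SAP bands equal the Appendix 1 erythema bands for Grades 1 to 3, so there is no discrepancy there.

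**Grade 4.** The SAP bands cannot produce Grade 4 for either sign, so those rows of Table 14.3.3.1 have no derivation behind them.

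**Effect of one participant.** Cohort sizes come from SAP Table 1, assuming every participant contributes swelling data. The shift in the swelling Grade 3 rate is 1/n:

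- n = 5 (cohorts 1 and 2): 1/5 = 20.0 points
- n = 6 (cohorts 3 and 4): 1/6 = 16.7 points
- n = 15 (cohorts 5 and 6): 1/15 = 6.7 points
- n = 52 (all participants): 1/52 = 1.9 points

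These are shifts per participant. Neither document says how often such a swelling should be expected.

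**The case against.** The strongest reply concerns the endpoint. The endpoint is Grade 3 or higher local and systemic reactions, not Grade 3 swelling. SAP 10.8.2 grades pain, warmth and eight systemic symptoms by function, with prevention of daily activities as Grade 3. Someone whose activity is prevented by a swollen arm may well record Grade 3 pain as well. Reactions lasting beyond 3 days become adverse events under the footnote to Protocol 7.3.1.1, are graded by Appendix 1, and enter the adverse event tables. This stands. A reader might infer that disabling swellings of 10 cm or less simply drop out of the primary endpoint, and the documents do not support that. The loss is in the swelling row, and reaches the participant level only when nothing else recorded is Grade 3.

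Second, the functional data may not exist. The listing shell has no functional item for swelling, and for induration Protocol 7.3.1.1 specifies only a diameter beyond its general request to grade severity. The investigator records reactions only on Day 0, with the post-dose assessment at the end of the observation period (Protocol 6.2), so that record cannot cover Days 1 to 3. This also stands. It limits the repair but makes disclosure more necessary.

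Third, Appendix 1 reproduces nonbinding guidance, and its footnote is worded as a recommendation. This carries less weight, because the functional criteria are in the table cells themselves and Protocol 8.2.3.1 adopts that table as the study's scale.

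Fourth, Section 11 covers changes to the protocol-specified analysis, and Protocol 10.2.2.6.1 specifies no solicited-reaction table. That is arguable, but the grading scale is protocol-specified, and SAP 10.8.3 and 10.8.4 follow Appendix 1 for laboratory values and vital signs.

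Finally, the missing Grade 4 rule hides little. Necrosis would be expected to be reported as an adverse event, and severe local reactions are notified to the Safety Monitoring Committee (Protocol 8.1.4).

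**Conclusion.** The conflict is real and worth correcting. For swelling, the SAP rule gives a different and never higher grade than the protocol's own scale. Any swelling of 10 cm or less that prevents daily activity is Grade 3 under the protocol and Grade 0, 1 or 2 under the SAP.

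The size per affected participant is between 1.9 points (all 52) and 20.0 points (a cohort of 5) on the swelling Grade 3 rate. A reader might take the 20 points as an expected bias in the primary endpoint. It is not: it assumes that one such participant occurs. It carries over to the endpoint as a whole only if that participant has no other Grade 3 reaction item or adverse event record. Nor does the shared size rule mean that redness is misgraded, since it matches Appendix 1 for Grades 1 to 3.

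The conclusion rests on reading Protocol 8.2.3.1 and 7.3.1.1 together as making Appendix 1 the scale for solicited reactions. It does not depend on whether function was in fact collected for swelling. That decides only which remedy is available.

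**What to change.** 1. In SAP 10.8.2, derive the swelling grade as the worse of the size grade and any functional severity recorded for swelling. Possible sources are the diary grade under Protocol 7.3.1.1, the Day 0 investigator record and the adverse event record. Keep size-only grading for redness Grades 1 to 3.
2. Take Grade 4 from adverse event records: necrosis for swelling, and necrosis or exfoliative dermatitis for redness.
3. If function was not collected for swelling on Days 1 to 3, label the swelling grades as size-only, state that they can under-grade relative to the protocol scale, and declare this in SAP Section 11.
4. In either case, replace the functional severity key under Table 14.3.3.1 for swelling and redness with the criteria actually used.

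The cost is one derivation rule, a table footnote and, if step 3 applies, a Section 11 entry. The drawback is that the corrected grade is only as complete as the functional data recorded for swelling. The listing shell suggests these may be sparse, in which case disclosure does most of the work.
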